3. Ventilator-free days (VFD) up to 28 days or hospital discharge

VFD will be analyzed for both all patients as well as for the subgroup of patients who were alive at Day 28 or hospital discharge. For the analysis of all patients separate analyses will be conducted for patients who died: a) VFD will be set to 0, b) the observed VFD until death will be considered. Summary tables will be generated the VFD will be compared using Wilcoxon rank sum test. In addition, bootstrap methods will be applied to calculate 95% confidence intervals and two-sided p-values for the difference in means.

4. Proportion of responders, defined as ≥ 2 improvement in WHO's 11-Point Score system at day 7, 10, 14 and 28

Similar analyses as for 28-day mortality will be conducted.

5. Time to death (all cause) will be analyzed using Kaplan-Meier estimates and plots, log-rank test, and Cox proportional hazards model (adjusted for minimization factors to derive hazard ratios and corresponding 95% confidence intervals). Patients who will be alive at Day 28, or who will be discharged from hospital before day 28 with no information on death until day 28, will be censored at discharge if they cannot be reached at or after day 28 by means of a telephone interview. Further details will be described in the statistical analysis plan.

6. Proportion of patients with any use of invasive mechanical ventilation up to 28 days or hospital discharge

Similar analyses as for 28-day mortality will be conducted.

7. Time to first use of invasive mechanical ventilation up to 28 days or hospital discharge
Similar analyses as for time to death will be conducted. Patients without invasive mechanical ventilation will be censored on the last day of evaluation. For patients who died the observed time to first use of invasive mechanical ventilation will be considered; if a patient who died did not receive any mechanical ventilation, the patient will be censored on time of death.

8. Absolute values and absolute change in P/F ratio over time

The PF ratio is defined as PaO₂ [mmHg] divided by FiO₂ in [%] and will be evaluated on each visit. Summary statistics for the PF ratio for both the absolute values and the absolute change from Baseline (day 1) will be tabulated.

9. Absolute values and absolute change in the modified Sequential organ failure assessment score (mSOFA score) over time

Similar analyses as for the PF ratio will be conducted.

10. Time to a 2-point decrease in WHO scoring scheme.

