The odds ratio along with its associated 95% confidence intervals will be reported.

Ventilator-free days (VFD) (up to 28 days or hospital discharge)

VFD will be calculated as follows:

$VFD = \text{maximum}((\text{Duration in the study [days]} - \text{Duration of ventilation [days]}); 0)$

i.e. if the duration of ventilation is greater than the duration in the study, VFD is set to 0.

Duration in the study [days] = Date of study completion/ discontinuation - Date of randomization + 1.

Patients who died before or on Day 28 will be censored at the day before death (Date of death - 1).

Duration of ventilation [days] = Sum of days with all required ventilations.

If ventilation started before randomization, the duration will be counted from the date of randomization. If ventilation started and/or ended after study completion/ discontinuation, the duration will be counted until date of study completion/ discontinuation.

If ventilation is ongoing and/or no stop date is available, the duration will be calculated until date of study completion/ discontinuation or date of death respectively.

VFD will be analyzed for both all patients as well as for the subgroup of patients who were alive at Day 28 or hospital discharge/early termination. For the analysis of all patients separate analyses will be conducted for patients who died: a) VFD will be set to 0, b) the observed VFD until death will be considered.

Summary tables will be generated by treatment group.

VFD will be compared using Wilcoxon rank sum test at a significance level of 5% (two-sided) and p-value (two-sided) will be reported.

In addition, bootstrap methods will be applied to calculate 95% confidence intervals and two-sided p-values for the difference in means between treatment groups.

Proportion of responders, defined as >= 2 improvement in WHO's 11-Point Score system at Day 7, 10, 14 and 28

Patients who will be not assessed from any cause (e.g. discharge from hospital, early termination, death or in-home visit) will be considered as non-responder.

Chi-squared test or Fisher's exact test

Proportion of responder, i.e. those patients that have >= 2 improvement in WHO's 11-Point Score system, as well as the p-value (two-sided) will be reported for Day 7, 10, 14 and 28.

Logistic regression

The following co-factors will be included in the logistic regression:

- ❑ Arterial hypertension
- ❑ Diabetes
- ❑ Coronary artery disease

- Age (<65 years vs. ≥65 years)
- Center

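### Three ventilator-free-day analyses are planned with no lead: one can rank a death above survival and another compares survivors only, so the VFD result can mislead or be quoted selectively

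*SAP*

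**What the plan says.** SAP 4.4.2 (ventilator-free days) defines VFD as days in the study minus days ventilated, with a floor at zero: "if the duration of ventilation is greater than the duration in the study, VFD is set to 0". For a patient who dies by Day 28, days in the study stop on the day before death.

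Three analyses follow:

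- **All patients, two versions.** They differ in how deaths are scored: "a) VFD will be set to 0, b) the observed VFD until death will be considered".
- **Survivors only.** VFD is also analysed "for the subgroup of patients who were alive at Day 28 or hospital discharge/early termination".

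The groups are compared by a Wilcoxon rank sum test at a two-sided 5% level. In addition, "bootstrap methods will be applied to calculate 95% confidence intervals and two-sided p-values for the difference in means between treatment groups".

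The protocol has the same plan in the synopsis and in 8.7.1.2.5, endpoint 3: "For the analysis of all patients separate analyses will be conducted for patients who died", the second being "b) the observed VFD until death will be considered". Neither document calls any version main, supportive or a sensitivity analysis, and SAP section 5 (changes from protocol) does not mention VFD. SAP 3.4 bases efficacy analyses on the full analysis set (FAS). That may favour all patients over the survivor subgroup, but it cannot choose between (a) and (b), because both use all patients.

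**The concern.** The three versions answer different questions and can disagree in size and in sign.

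Version (b) credits a patient with the days off the ventilator before death. Someone who dies late without being ventilated can therefore score better than someone who was ventilated and recovered. The survivors-only version conditions on an outcome that the treatment may change. If one arm loses more of its sickest patients, its survivors look healthier, and the comparison can favour the arm with higher mortality.

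With no lead named, the version to emphasise can be chosen after unblinding. At stake is how the VFD result is read and reported.

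**Working it through.** **The plan's own figure.** The documents give no power, effect size or SD for VFD. The only power figure is for the primary composite: 93 per group, 80% power, 50% against 30%, two-sided 0.05 (protocol 8.7.2). With a pooled rate of 0.40:

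n = [1.96 × √(2 × 0.40 × 0.60) + 0.8416 × √(0.25 + 0.21)]² / 0.20² = (1.358 + 0.571)² / 0.04 ≈ 93.

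It reproduces and is not at issue. All VFD inputs below are assumptions, apart from the 100 per arm that the protocol plans to enrol.

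**1. Ranking under (b)** (SAP formula, randomised on Day 1, 28 days of study)

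- Unventilated, dies on Day 20: counted to Day 19, so VFD = 19 − 0 = 19. Under (a) it is 0.
- Survivor ventilated for 12 days: VFD = 28 − 12 = 16.

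Under (b) the death ranks higher.

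**2. Dilution.** Suppose nobody is ventilated and one arm has 10 percentage points more deaths, all on Day 20. Mean VFD in that arm is lower by:

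- (a): 0.10 × 28 = 2.8 days
- (b): 0.10 × (28 − 19) = 0.9 days
- survivors only: 0

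**3. Sign.** Take 100 per arm, with 15 deaths on APN01 and 25 on placebo. Ventilated survivors number 35 and 25, each ventilated for 14 of 28 days. The other 50 in each arm survive unventilated.

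| Version | APN01 | Placebo | Difference |
|---|---|---|---|
| (a) | (50×28 + 35×14)/100 = 18.9 | (50×28 + 25×14)/100 = 17.5 | +1.4 |
| (b), 3 days credited per death | 18.9 + 0.15×3 = 19.35 | 17.5 + 0.25×3 = 18.25 | +1.1 |
| (b), 10 days | 20.4 | 20.0 | +0.4 |
| (b), 20 days | 21.9 | 22.5 | −0.6 |
| Survivors | 1890/85 = 22.2 | 1750/75 = 23.3 | −1.1 |

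The arm with fewer deaths looks better or worse depending on the version.

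**4. Simulated power** (Wilcoxon, 100 per arm, mortality 15% against 30%, equal ventilation among survivors)

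| Assumption about deaths | (a) | (b) |
|---|---|---|
| 30% ventilated, deaths on days 15-28 | 53% | 27% |
| 80% ventilated, deaths on days 2-28 | 53% | 46% |
| 80% ventilated, deaths on days 5-15 | 54% | 52% |

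Across the settings examined, (a) gave about 52-55% and (b) about 26-52%, a loss of roughly 2 to 29 points. These are ranges over assumptions, not bounds. The survivors-only test rejected in about 5%, as it must when ventilation among survivors is set equal.

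**5. Simulated harm** (mortality 25% on APN01 against 10%, survivors ventilated 15% against 30%, deaths on days 5-27, ventilated survivors 5-20 days on the ventilator, 0-80% of deaths ventilated). Mean difference, APN01 minus placebo: (a) about −2.2 days; (b) −1.3 to 0.0; survivors about +1.9 days in favour of APN01, with p<0.05 in about 61-64% of runs.

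**6. No effect** (20% mortality and 25% of survivors ventilated in both arms). Each Wilcoxon test rejected in about 5% of runs. At least one of the three was below 0.05 in about 9-10%. If each version also gets a bootstrap p-value, there are 3 × 2 = 6; the bootstrap tests were not simulated.

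**The case against.** - **Mortality is not hidden in the trial.** A reader might infer that it could be. The documents do not support that: death is part of the primary composite (SAP 4.4.1), is tested alone as 28-day mortality, and again as time to death by log-rank and Cox (SAP 4.4.2). Version (a) is itself planned. The dilution is confined to two of the three VFD displays. This stands.
- **VFD is exploratory.** Protocol 8.7.1.2.5 treats all secondary endpoints that way, and all three versions were fixed before unblinding. The 9-10% figure therefore breaches no stated error control. This stands too. What remains is selective emphasis among pre-specified analyses, which naming a lead would remove.
- **Version (b) is a valid comparison.** It is tempting to say that it is no treatment comparison at all. That goes too far: it keeps every randomised patient in the assigned arm and rejects at about 5% under no effect. It gives death less weight than (a), which is a choice of what to estimate. The objection that a comparison is not randomised applies only to the survivors-only version.
- **The text is not fully explicit.** The SAP does not say in terms that every version gets both tests, and Appendix A, which describes the tables, is not among the documents supplied. Six p-values is the natural reading, but an inference.

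**Conclusion.** The point holds for VFD. Three analyses that can differ in sign are planned without a lead; (b) can rank a late unventilated death above a ventilated survivor, and the survivors-only comparison can favour the arm with higher mortality. The ranking and the sign reversal follow from the SAP's own formula. The power figures rest on assumed mortality, timing of death and ventilation among deaths, so no single figure for the power loss under (b) is supported: it ranges from negligible to about half of the power of (a).

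This is a cheap improvement to an exploratory endpoint. It does not threaten the primary analysis or the reporting of mortality.

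**What to change.** In SAP 4.4.2:

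- Name (a), deaths scored 0, in the FAS with the Wilcoxon test as the lead VFD analysis. Use the bootstrap 95% confidence interval for the difference in means as its estimate.
- Label (b) as supportive.
- Show the survivors-only version descriptively, without a p-value, and state that it is not a randomised comparison.

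Because the protocol carries the same three unranked analyses, record the change in SAP section 5. No new data, visits or patients are needed. The small downside is that fewer VFD p-values are reported.

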8.5.2.2.10 WHO 11-point scale

The WHO Clinical Progression Scale (WHO-CPS) measures patient illness by tracking progress through the healthcare system. The WHO-CPS incorporates a number of explicit features that are advantageous for its use in emerging infectious disease epidemic. It provides a measure of illness severity across an 11 point range from 0 (not infected) to 10 (dead) (Annex 1).

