8.7.2 Determination of Sample Size

186 patients (93 per group) will yield 80% power to detect a 20% absolute risk reduction in the primary composite endpoint, from 50% in the placebo group to 30% in the APN01 group at a two-sided alpha of 0.05 when applying a two group Chi-Squares test. To consider patients who will be randomized but not treated a total of 200 patients (100 per group) will be enrolled.

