4.4.1 Analysis of Primary Efficacy Endpoint

The primary endpoint is a composite endpoint of all cause-death or invasive mechanical ventilation (up to 28 days or hospital discharge).

The following null hypothesis will be tested:

- $H_0: p_{APN01} = p_{Placebo}$

versus the alternative

- $H_1: p_{APN01} \neq p_{Placebo}$

H_0 will be tested using a Chi-squared test. The level of significance is 5% (two-sided). In addition, logistic regression analyses will be conducted considering additional co-factors.

All cause-death

The percentage of patients who have died at Day 28 will be presented by treatment group.

Patients with death from any cause will be used for this endpoint as part of responder. Patients who are still alive at Day 28 will be considered as non-event.

The following cases may occur:

- Patient discharged from hospital **and** discontinued before Day 28, will be followed up by telephone interview to check whether they are alive or dead, if unclear as no telephone interview available, death is assumed (worst case) at last available date of early termination, hospitalization or hospital discharge
- No discharge from hospital, **but** early discontinuation before Day 28 will be followed up by telephone interview to check whether they are alive or dead, if unclear as no telephone interview available, death is assumed (worst case) at date of early termination
- Discharged from hospital, **but** no discontinuation before Day 28: No telephone interview, but regular entry at Day 28 about alive/death status

Invasive mechanical ventilation (up to 28 days or hospital discharge)

Invasive mechanical ventilation is defined as patients who are intubated or have a tracheostomy tube and are receiving positive pressure ventilation. Patients with at least one invasive mechanical ventilation (event with type of ventilation 'Mechanical ventilation') up to 28 days or hospital discharge will be used for this endpoint as part of responder.

Chi-squared test

Proportion of responder, i.e. those patients that died or having an invasive mechanical ventilation (up to 28 days or hospital discharge), as well as the p-value (two-sided) will be reported.

Logistic regression

A logistic regression with the responder (yes/no) as independent variable will be applied.

The following co-factors will be included in the logistic regression:

- Arterial hypertension

- ❑ Diabetes
- ❑ Coronary artery disease
- ❑ Age (<65 years vs. >=65 years)
- ❑ Center

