Absolute values and absolute change in PaO2/FiO2 ratio over time

The PaO2/FiO2 ratio = PaO2 [mmHg] / FiO2

This will be evaluated on each visit for ventilated patients only. If entries are not changed compared to previous entries, no entry will be done within the eCRF.

If ventilation is ongoing and/or no stop date is available, the PaO2/FiO2 ratio will be considered until date of study completion/ discontinuation or date of death respectively.

Baseline is defined as first observation of PaO2/FiO2 ratio (individual start value). Basic statistics for the PaO2/FiO2 ratio for both the absolute values and the absolute change from baseline will be tabulated by day of ventilation. Daily means will be used when more than one assessment is available per day.

Absolute values and absolute change in notified sequential organ failure assessment score (mSOFA score) over time

The mSOFA score was introduced with protocol version 5.0 and is available for patients who are included with protocol version 5.0 and higher. For patients who are included with previous protocol versions (protocol version 4.0 and lower), mSOFA score is available from the time when protocol is in effect at the centers.

Basic statistics for the mSOFA score for both the absolute values and the absolute change from baseline will be tabulated by visit.

SOFA score (protocol version 4.0 and lower) will be listed only.

Time to a 2-point decrease in WHO's 11-Point Score system

Time to 2-point decrease [days] = Assessment date of first ≥ 2 improvement - Date of randomization.

Patients without documented 2-point decrease who completed the study or was early terminated or discharged from hospital before Day 28 will be censored at the date of last WHO assessment available.

Time to 2-point decrease will be analyzed using Kaplan-Meier estimates and plots, log-rank test, and Cox proportional hazards model (adjusted for center and age to derive hazard ratios and corresponding 95% confidence intervals).

Kaplan-Meier estimates and Log-rank test

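### The 11-point WHO score is used only through a 2-point-improvement cut; adding a full-scale analysis would recover power at Day 7 and, depending on disease course, Day 10

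*SAP*

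**What the plan says.** Protocol 8.5.2.2.10 describes an ordinal scale: "It provides a measure of illness severity across an 11 point range from 0 (not infected) to 10 (dead"). Table 1 of the protocol schedules it at screening, daily on Days 1-7, and on Days 10, 14 and 28.

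Two secondary endpoints use it.

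- **Responder proportion.** For this endpoint Protocol 8.7.1.2.5 says "Similar analyses as for 28-day mortality will be conducted". SAP 4.4.2 specifies a chi-squared or Fisher test and a logistic regression, separately for each of the four days, of the "Proportion of responder, i.e. those patients that have >= 2 improvement in WHO's 11-Point Score system".
- **Time to a 2-point decrease.** SAP 4.4.2 defines the time as "Assessment date of first ≥ 2 improvement - Date of randomization" and uses Kaplan-Meier, log-rank and Cox methods.

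For the responder endpoint, SAP 4.4.2 also counts anyone not assessed at a visit as a non-responder, and lists hospital discharge and in-home visits among the reasons.

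Protocol Annex 1 fixes the categories: 0-3 uninfected or ambulatory, 4 in hospital without oxygen, 5 mask or nasal prongs, 6 NIV or high flow, 7-9 mechanical ventilation by severity, 10 dead.

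**The concern.** On Annex 1, a patient who enters at 5 responds only at 3 or below. In practice that means leaving hospital, apart from patients kept in only for isolation, who are scored as ambulatory. Being weaned off oxygen in hospital (4), no change (5), escalation (6), intubation (7-9) and death (10) become one category. A patient who enters at 6 responds at 4.

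The trial collects a graded outcome and then tests one split of it. When few patients have crossed the split, as early in follow-up, the yes/no test uses little of the information. If APN01 shifts patients along the whole scale, a null responder result at Day 7 or Day 10 could be read as no benefit on the WHO scale although the recorded scores show a shift. No comparative test elsewhere covers weaning from oxygen, or escalation to high flow or NIV, as such: P/F ratio is summarised for ventilated patients only, and type of ventilation is tabulated as frequencies.

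**Working it through.** **Inputs from the documents.** Two-sided 5% level (SAP 4.4.1). Planned rates "from 50% in the placebo group to 30% in the APN01 group at a two-sided alpha of 0.05". Enrolment: "a total of 200 patients (100 per group) will be enrolled".

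**The plan's own figure.** "186 patients (93 per group) will yield 80% power to detect a 20% absolute risk reduction in the primary composite endpoint". With n = [1.96·√(2p̄(1−p̄)) + 0.8416·√(p₁(1−p₁)+p₂(1−p₂))]² / (p₁−p₂)² and p̄ = 0.40:
(1.96×0.6928 + 0.8416×0.6782)² / 0.04 = 3.720 / 0.04 = 93 per group. It reproduces exactly; 100 per group gives 82.8%. No power is stated for the WHO endpoints.

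**Assumed effect.** The planned rates imply an odds ratio of (0.3/0.7)/(0.5/0.5) = 0.43 for a worse score, or 2.33 for a better one. It is applied as a common odds ratio across the scale, with 100 per arm. Discharged patients are taken as scored unless stated.

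**Set A (assumed).** 65% enter at 5 and 35% at 6; baseline effect 0.7 logits per point; scores 0-3 merged. Placebo distributions for baseline 5 over {0-3, 4, 5, 6, 7, 8, 9, 10}:

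- Day 7: .18, .12, .27, .15, .10, .08, .05, .05
- Day 10: .30, .10, .18, .10, .11, .08, .05, .08
- Day 14: .40, .08, .11, .06, .11, .08, .05, .11
- Day 28: .48, .05, .05, .03, .09, .07, .05, .18, and a more severe variant .38, .05, .04, .03, .13, .10, .07, .20

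Day 7 by hand:

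- Placebo, baseline 5: P(0-3) = 0.18. Baseline 6: P(0-4) = expit(logit 0.30 − 0.7) = 0.1755. Responders: 0.65×0.18 + 0.35×0.1755 = 17.8%.
- APN01: add ln 2.333 = 0.847 to each logit, giving 0.3387 and 0.3318. Responders: 33.6%.
- Chi-squared power: Φ{[10×0.158 − 1.96×0.618] / 0.608} = Φ(0.60) = 73%.

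Simulated power (4,000 trials), responder chi-squared vs baseline-stratified Wilcoxon (van Elteren) on the full score:

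| Day | OR 0.43 | OR 0.55 | OR 0.60 |
|---|---|---|---|
| 7 | 73% vs 92% | 43% vs 66% | 31% vs 53% |
| 10 | 81% vs 91% | 50% vs 65% | 38% vs 52% |
| 14 | 86% vs 89% | 55% vs 63% | 45% vs 51% |
| 28 | 84-85% vs 88-90% | 54-57% vs 62-63% | 42-45% vs 49-52% |

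Stratifying the responder test by baseline changes almost nothing (Day 7, OR 0.43: 72.8% vs 73.2%), so the gain comes from the scale.

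**Set B (assumed).** A severe and a milder course, with 50-90% entering at 5. With 70% at 5, responders at Day 7 are 10% vs 21% (severe) and 19% vs 36% (milder). Odds ratio 2.33; responder test vs unstratified Wilcoxon:

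| Day | Severe | Milder |
|---|---|---|
| 7 | 55-56% vs 89-90% | 74-75% vs 87-90% |
| 10 | 74-75% vs 90-92% | 84% vs 87-88% |
| 14 | 82-83% vs 90% | 80-81% vs 82-85% |
| 28 | 81-82% vs 83-85% | 59-65% vs 59-70% |

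The losses are about 12-35, 3-17, 2-8 and 0-5 points. At odds ratio 2.0 they are 14-39, 6-21, 2-12 and 0-5.

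**Why early.** The efficiency of a yes/no split relative to the full scale is about 3p(1−p)/(1−Σpᵢ³), where p is the average response proportion. With Σpᵢ³ between 0.05 and 0.20 this is 0.40-0.48 at p = 0.15 and 0.79-0.94 at p = 0.50.

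**Time to a 2-point decrease.** Taking HR = ln(1−p_APN01)/ln(1−p_placebo) from Set B Day 28 responders, for example 51% vs 71%: HR = 1.74, 122 events, power Φ(√122/2 × ln 1.74 − 1.96) = 86%. Across Set B it is about 65-86%, against 59-85% for the Day 28 full-scale test.

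**Other effect patterns.** If the drug changes only the bad outcomes, the responder test stays at 5%; the full-scale test has 17-45% (Set A) or 6-27% (Set B). If it changes only discharge, the responder test wins: at Day 7, 47% vs 9% (Set A) or 82% vs 17-37% (Set B).

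**The unassessed-patient rule.** If half of discharged patients are not assessed (an assumption), responder power at odds ratio 0.43 is about 37-44% at every visit in Set A. In Set B it is 31-50%, 41-48%, 28-46% and 13-33% at Days 7, 10, 14 and 28.

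**The case against.** - **These are exploratory endpoints with no power claim.** True. Power is stated for the primary endpoint, and only LDH is labelled a powered secondary endpoint. No stated figure is contradicted, and a 2-point responder is a legitimate protocol-defined endpoint.
- **Death and intubation are tested elsewhere.** True. They form the primary composite, and SAP 4.4.2 adds mortality, ventilator-free days, time to death, invasive ventilation and time to discharge. A reader might infer that the plan is blind to death and ventilation; it is not. What no other comparative test covers is movement between 4, 5 and 6.
- **The ventilation boundary can enter the responder analysis.** SAP 4.4.2 provides for patients ventilated before randomisation. For them a move from 8 to 6, or from 7 to 5, is a response. The loss of information described here concerns patients entering at 5, and the calculations cover entry at 5 or 6 only.
- **The distributions are invented and the sign can reverse.** Both stand, which is why the size is a range and the responder test is kept.
- **The power comparison is not the planned test, because unassessed patients are non-responders.** This stands. The main comparison assumes discharged patients are scored. Under the rule as written, the larger shortfall can fall at Days 14 and 28, and that part comes from the rule and not from the cut.
- **Appendix A is unavailable.** A tabulation of the score may be listed there, so its absence cannot be confirmed.

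**Conclusion.** The point holds in a limited form. In the SAP text supplied, the WHO score is analysed only through a 2-point-improvement cut, and for a patient entering at 5 very different outcomes are one non-response at a visit. Under proportional odds at the planned odds ratio and assumed distributions, the visit-specific responder test loses about 12-35 points of power at Day 7, 3-17 at Day 10, and less than about 10 at Days 14 and 28.

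A reader might infer that much of the power of all the WHO analyses is lost. The calculations do not support that: the loss is substantial only at Day 7 and, on a more severe course, Day 10, and none is shown for the time to a 2-point decrease. Nor do they support making a full-scale analysis the lead and demoting two protocol-defined endpoints, since the full-scale test is much weaker if the drug acts only on discharge.

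This is a cheap improvement, not an error that threatens the trial's main conclusion.

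**What to change.** In SAP 4.4.2, add a supplementary full-scale analysis of the WHO score in the FAS at Days 7, 10, 14 and 28:

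- a proportional-odds model with treatment, baseline WHO score and the randomisation factors (age, and centre, pooled if sparse), reporting the common odds ratio with 95% CI;
- a van Elteren p-value stratified by baseline score, which does not need proportional odds;
- deaths scored 10 at all later visits;
- scores 0-3 merged as alive and not hospitalised, with discharged patients known to be alive placed there even without a score at that visit;
- a table of the score by arm and day.

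Keep the responder proportion and the time to a 2-point decrease as planned, and record the addition in SAP section 5.

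The cost is SAP wording and modest programming before unblinding, with no new data, visits or patients. The downsides are a few more exploratory estimates, and lower power than the responder test if the effect is only on discharge timing.
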